1.0 SYNOPSIS

Title:	EnSite Precision™ Cardiac Mapping System and EnSite Precision™ Software v2.0 Observational registry
Acronym:	EnSite Precision™ 2.0 Registry
Purpose:	The purpose of the registry is to collect data on the EnSite Precision™ Cardiac Mapping System and EnSite Precision™ Software v2.0. This data will be used to evaluate its clinical performance.
Objectives:	The objective of this registry is to assess and characterize the use and performance of the EnSite Precision™ Cardiac Mapping System and the EnSite Precision™ Software V2.0 in a variety of electrophysiological (EP) procedures and clinical settings. This registry will assess the clinical performance of the system in a controlled, real-world environment after commercial release.
Endpoints:	
The assessments on the system will include the following:
 
 - EnSite Precision™ Cardiac Mapping System Assessment - EnSite Precision™ Software V2.0 Assessment - AutoMap™ Module Assessment - AutoMark feature Assessment 
The descriptive endpoints for characterizing and evaluating the system are as follows:
 
Primary Endpoints:
 
 - EnSite Precision™ Software V2.0 Assessment 
 o Accuracy of geometry o Overall system stability o Unrecoverable shifts - AutoMap™ Module Assessment 
 o Mapping time associated with (re-)mapping one or multiple arrhythmias in a single patient with a variety of catheters 
 ▪ Manual mapping ▪ AutoMap™ ▪ TurboMap™ o Point density associated with (re-)mapping one or multiple arrhythmias in a single patient with a variety of catheters 
Secondary Endpoints:
 
 - EnSite Precision™ Cardiac Mapping System Assessment 
 o Ease of use o Overall procedure time - AutoMark feature Assessment 
 o Clinical Utility of the automated RF marker placement o Ease of Use of the automated RF marker placement

Clinical Investigational Plan

[figure not shown]
Design:	
This is a multi-center, observational, prospective registry.
 
Up to 500 subjects will be enrolled in up to 50 sites worldwide.
 
Data will be collected at enrollment/baseline, procedure and pre-discharge. There is no long-term follow-up required for this registry.
 
The anticipated registry enrollment is about 6-7 months.

Devices used:	
All devices must have CE mark and will be used according to their Instructions for Use (IFU).
 
This comprises: The EnSite Precision™ Cardiac Mapping System and software v2.0, which consists of:
 
 - EnSite Precision™ software 2.0 - EnSite Precision™ Module, Sensor Enabled - EnSite Precision™ Surface Electrode Kit - AutoMap™ Module - AutoMark feature - Advisor™ FL Circular Mapping Catheter, Sensor Enabled™ and/or FlexAbility™ SE Ablation Catheter 
Additional tools that may be used in this registry (per physician's discretion), include, but are not limited to:
 
 - Tacticath™ Ablation Catheter - FlexAbility™ Ablation Catheter - MediGuide™ Platform - Other commercially available catheters to facilitate EP procedures 
The EnSite™ Amplifier and Display Work Station, required to support the system, will not be evaluated under the scope of this registry.

Registry Population	
A patient becomes a subject once he/she has been fully informed about the registry, has agreed to participate and signed & dated the Informed Consent Form (ICF).
 
Any patient undergoing a cardiac EP mapping and ablation procedure, using the EnSite™ Precision Cardiac Mapping system, is considered eligible.

Inclusion/Exclusion Criteria	
Inclusion Criteria
 
 - Patients indicated for a cardiac EP study and ablation procedure using a 3D mapping system - Over 18 years of age - Ability to provide informed consent for registry participation and be willing and able to comply with the protocol described evaluations 
Exclusion Criteria
 
 - Contraindication to anticoagulation - Presence of thrombus

Clinical Investigational Plan

	
 - Implanted with mechanical prosthetic heart valve - Recent (<3 months) myocardial Infarction or unstable angina or coronary artery by-pass - Pregnant or nursing - Individuals whose willingness to volunteer in a registry, in the judgement of investigator or public authorities, could be unduly influenced by lack of or loss of the autonomy due to immaturity, or mental disability, or adverse personal circumstances, or hierarchical influence
Data Collection	
The use of the EnSite Precision™ Cardiac Mapping System will be assessed by collecting feedback from physicians/operators through specific questions.
 
The performance of the EnSite Precision™ Cardiac Mapping System will be assessed by collecting procedure data and adverse events.

1.1 Registry Flow Chart

Clinical Investigational Plan

2.0 BACKGROUND AND JUSTIFICATION FOR REGISTRY

In the last 20 years, atrial fibrillation (AF) has become one of the most important public health problems and a significant cause of increasing health care costs in Western countries. The prevalence of AF can be estimated at 2%, together with an incidence ranging between 0.23 and 0.41 per 1000 person/years. The number of hospitalizations for AF is 0.25 per year and the number of outpatient contacts is approximately 6 per year. This means that at the present time in the European community, there are approximately 10 million patients with AF and 100 000 - 200 000 with new onset AF. If the estimated prevalence of AF increases by an average of 0.4%, in 2030 the prevalence of AF would be 2.7%-3.3% in a European population with 516-525 million inhabitants^[1]. While paroxysmal AF ablations are the most common, the more challenging and less successful procedure is the persistent AF ablation procedure—making up 36%²- 45% of all of AF ablations, which is expected to increase over time^{[2][3]}.

Additionally, sudden cardiac death rates range from 50 to 100 per 100 000 in the general population^[4]. It is most commonly caused by ventricular tachycardia (VT) deteriorating into ventricular fibrillation (VF), which is fatal within a few minutes if not defibrillated back into a normal rhythm. There are three treatment options for VT, although many patients require a combination: an implantable cardioverter defibrillator (ICD), antiarrhythmic medication and catheter ablation^[5]. Usually, a combination of these treatments is the preferred therapy. Ventricular tachycardias (VT) are on the rise, with 56 000 ablation procedures worldwide^[6].

The increase in use of both of these ablation types represents an opportunity for the electrophysiology (EP) specific 3D mapping systems due to the increased case complexity and duration—as mapping system precision is a key requirement to maximize the success of these challenging procedures. As a result, the EnSite Precision™ System was developed to introduce features such as DE-MRI image integration, lesion marking automaticity, automatic mapping, and workflow flexibility to aid in the success of complex ablation procedures, including persistent AF and VT.

The registry is designed in such a way as to ensure that the results obtained have clinical relevance and scientific validity and address the registry objectives.

Clinical Investigational Plan

3.0 REGISTRY DESIGN

3.1 Purpose

The purpose of this registry is to collect data on the EnSite Precision™ Cardiac Mapping System and EnSite Precision™ Software V2.0. This data will be used to evaluate its clinical performance.

3.2 Design and Scope

This is a multicenter, observational, prospective registry. The purpose is to characterize data and information collected on the performance of the EnSite Precision™ Cardiac Mapping System and EnSite Precision™ Software v2.0.

The total duration of the registry is expected to be about 1 year. This includes subject enrollment duration, procedure visit, pre-discharge visit and time to close the registry and provide a final report.

As no follow up period is required for this registry, the subject participation will end upon completion of the pre-discharge visit.

3.2.1 Number of subjects required to be included in the registry

Up to 500 subjects will be enrolled in up to 50 sites worldwide. No site can enroll more than 15% (i.e. 75 patients) of the sample size.

Each site is allowed to enroll subjects with any arrhythmia qualified for ablation.

NOTE: A variety of arrhythmias (atrial and ventricular in origin) is strongly recommended.

3.2.2 Estimated time needed to enroll this subject population

The anticipated enrollment duration is roughly 6-7 months. No long-term follow-up is required for this registry.

3.3 Objectives

3.3.1 Objective

The objective of this registry is to assess and characterize the use and performance of the EnSite Precision™ Cardiac Mapping System and the EnSite Precision™ Software V2.0 in a variety of EP procedures and clinical settings. The registry will assess the clinical performance of the system in a controlled, real-world environment after commercial release.

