5.5 Procedure Visit (within 14 days from Baseline visit)

The procedure should be performed according to the instructions for use (IFU) of the EnSite Precision™ Cardiac Mapping System, the IFU of AutoMark feature and AutoMap™ and other medical devices used during the procedure.

Subjects will be prepared according to the standard surgical procedures and standard practice of the center. The procedure should always be done with the aid of fluoroscopy.

Instances where fluoroscopy images should be collected and uploaded via Electronic Data Capture (EDC):

- At procedure start, after initial catheters are in place. Consider placing catheters in reproducible locations within the chamber of interest.
- At procedure end, prior to removal of catheters. Replicate catheter location(s) used previously.
- At any point during the procedure where an instance of instability might have occurred. Replicate catheter location(s) used previously.

The anonymized images should be uploaded using following naming convention:

- SiteID_PatientID_Fluoro Procedure Start
- SiteID_PatientID_Fluoro Procedure End
- SiteID_PatientID_Fluoro Procedure Instance of Instability

(in case of multiple possible instances, please number them accordingly)

Please refer to the Procedure Guidelines (provided in a separate document) for more detailed information.

Concerning additional data collection, please refer to the procedure guidelines. These guidelines are not mandatory, however, they may assist in current knowledge and understanding of the treatment options for patients with arrhythmias.

The entire study (EPS) should be backed up on a USB drive (provided by sponsor) and returned to the sponsor within reasonable timelines. Please refer to the Procedure Guidelines for additional information.

The User Experience Form should be completed once by every physician performing a procedure for this registry.

Clinical Investigational Plan

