5.7 Description of Activities performed by Sponsor Representatives

Trained sponsor personnel may perform certain activities to ensure compliance to the clinical investigational plan and may provide technical expertise.

Sponsor personnel will not:

- Administer the informed consent process
- Practice medicine
- Provide medical diagnosis or treatment to subjects
- Discuss a subject's condition or treatment with a subject without the approval and presence of a health care practitioner
- Independently collect registry data

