8.6 Steps that will be taken to control or mitigate the Risks

Every possible effort will be taken to minimize the risks, including:

- Careful selection of experienced investigators who have experience with EnSite Precision™ V2.0 Cardiac Mapping System and study teams for the registry
- Conduction of the ablation procedures in accordance with the IFU of the corresponding devices

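### The real-world objective does not say that operators are selected for V2.0 experience, and the time and ease-of-use summaries take no account of experience or sponsor support

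*Combined protocol and SAP*

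**What the plan says.** The objective in 3.3.1, repeated in the synopsis, reads: "The registry will assess the clinical performance of the system in a controlled, real-world environment after commercial release". The same section says that this will be done "in a variety of EP procedures and clinical settings".

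Two other sections bear on who operates the system and with what help:

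- Section 8.6 lists as a risk-mitigation step: "Careful selection of experienced investigators who have experience with EnSite Precision™ V2.0 Cardiac Mapping System and study teams for the registry". It gives no minimum number of cases.
- Section 5.7 states: "Trained sponsor personnel may perform certain activities to ensure compliance to the clinical investigational plan and may provide technical expertise".

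Section 5.9 says that all foreseeable factors that could compromise the outcome have been considered, and lists recruitment plans, too little variety of arrhythmias, and enrollment targets. The only method in 5.10 is a screening tool based on arrhythmia history.

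In 12.1, mapping time is summarised by module (manual, AutoMap, TurboMap) and by arrhythmia type. Procedure time has one overall summary, and ease of use is given as a proportion of subjects in each rating category. Section 12.7 pre-specifies no subgroups and allows optional summaries by center and gender. On ratings, 5.5 says: "The User Experience Form should be completed once by every physician performing a procedure for this registry".

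**The concern.** Mapping time, procedure time and ease of use depend on the person at the controls. The plan's own description of AutoMap (notes to 5.5) says that points are collected under settings chosen by the user, as the catheter is moved. If operators are chosen because they know V2.0, and some have sponsor help, the summaries describe that group. A reader told only that the setting was real-world could apply them to a center taking up the system for the first time.

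The comparison of modules is also exposed. If operators turn to AutoMap or TurboMap as they gain experience, differences between modules and differences between stages of experience cannot be told apart.

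The results are to be published (section 17), and the data may support a market-approval application (section 9), so the population to which they apply should be stated correctly.

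**Working it through.** **1. The plan's own figures.** Section 12.2 wants at least 50 subjects per arrhythmia type and expects ventricular tachycardia in 10%: 50 / 0.10 = 500, as stated. The site cap is 0.15 × 500 = 75, also as stated. Neither depends on operator experience or support, and 12.10 rules out hypothesis testing. The point therefore concerns what the results describe, and changes neither the sample size nor any error rate.

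**2. Where each factor appears.**

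| Factor | Foreseen in | Visit schedule (Table 2, 5.3 to 5.6) | 5.9 and 5.10 | 12.1 and 12.7 |
|---|---|---|---|---|
| Operator's V2.0 experience | 8.6 | no item | not listed | not used |
| Sponsor technical support | 5.7 | no item | not listed | not used |

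The optional summary by center does not fill the gap: it separates neither operators within a center, nor early from late cases, nor supported from unsupported ones.

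**3. Cases per operator.** With both maxima reached, the mean is 500 / 50 = 10 per site. But 12.11 allows 1 to 75 per site, and 500 / 75 = 6.7, so as few as 7 sites could supply all subjects. The number of operators per site is not given, so cases per operator cannot be derived.

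**4. What the size would depend on.** Take two groups as a simplification. Experienced operators have mean time m, inexperienced ones m + d, and a fraction p of registry cases come from the second group. Then:

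- pooled registry mean = m + p·d
- mean for a new user = m + d, if new users resemble the inexperienced group
- gap = (1 − p)·d

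If p is near 0, the pooled figure describes experienced users and the gap is close to d. If p is large, the gap shrinks, but learning is then mixed into the pooled figure. The documents give neither p nor d, and no counterpart for support, so no gap can be calculated.

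**5. Ease of use.** Section 12.1 counts subjects, whereas the User Experience Form is completed once per physician. If the rating comes from that form, there is one rating per physician, and it cannot be split by case number or by support at a given case.

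**6. Cell sizes for a remedy.** With three modules and two experience bands, an even split (an assumption, with one module per subject) gives 500 / 6 = 83 subjects per cell overall, but only 50 / 6 = 8 within ventricular tachycardia. A table across arrhythmia types is workable; one within each type would be thin.

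**The case against.** The objective says controlled as well as real-world, and makes no claim about new users. The registry is descriptive, with no pass/fail criteria. Section 8.6 is a risk-mitigation step and sets no eligibility rule for operators; 8.1 describes the subjects simply as treated at centers equipped with the system. On support, 5.7 says only that staff "may provide technical expertise", and the acts it forbids them include "Independently collect registry data". Sections 8.2 and 8.4 say that the registry follows local practice and adds no procedures of its own. The CRFs and procedure guidelines are under separate cover and may already capture both items.

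Most of this stands, and it rules out three stronger readings:

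- A reader might infer that the results describe sponsor-supported users. The documents permit support; they do not say how often it occurs, or that it exceeds the support given outside the registry.
- A reader might infer that entry is restricted to highly practised operators. Without a threshold, experience could range from slight to extensive.
- A reader might put a percentage on the understatement from an assumed learning curve. The documents give no learning-curve input, so the result would only restate the assumption.

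The word controlled does not tell a reader how operators were chosen. And even if the CRF captures experience and support, section 12 plans no use of them.

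**Conclusion.** The concern holds as a limit on generalisability and reporting. The plan foresees selection for V2.0 experience and possible sponsor help, leaves both out of its list of factors affecting interpretation, and summarises operator-dependent endpoints without regard to either. The time and ease-of-use figures may therefore not carry over to users new to V2.0.

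The size is unknown. A favourable direction is plausible, but the documents do not establish it. The conclusion assumes only that these endpoints depend to some degree on the operator, which the AutoMap description supports. Selecting experienced investigators may well be sound risk mitigation, and nothing here argues against it. The change is worth making because it is cheap and because experience and support are hard to reconstruct afterwards.

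**What to change.** 1. State in 3.3.1, the synopsis and the report that results apply to operators selected for V2.0 experience.
2. Unless the CRF already does so, record each operator's number of V2.0 cases before the registry. Order each operator's registry cases by procedure date. Add to 12.1 a descriptive summary of mapping time (by module) and procedure time by cumulative V2.0 experience, with cut-points fixed before analysis.
3. Unless already captured, record for each case whether sponsor personnel gave technical support in operating the system, and report the time endpoints by that flag.
4. If ease of use comes from the User Experience Form, summarise it per physician, by experience when the form was completed, and not per case.
5. Add both factors to 5.9.

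The cost is some rewording, at most one operator-level field and one yes/no field per case, and one descriptive table. The downsides are a slightly narrower claim and small cells, especially within the less common arrhythmias; showing counts with every summary and keeping the table across arrhythmia types limits the second.

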3.4 Endpoints

The assessments on the system will include the following:

- EnSite Precision™ Cardiac Mapping System Assessment
- EnSite Precision™ Software V2.0 Assessment
- AutoMap™ Module Assessment
- AutoMark feature Assessment

The endpoints for characterizing and evaluating the system are as follows:

3.4.1 Primary Endpoints

- EnSite Precision™ Software V2.0 Assessment
 - o Accuracy of geometry
 - o Overall system stability
 - o Unrecoverable shifts

Clinical Investigational Plan

- AutoMap™ Module Assessment
 - o Mapping time associated with (re-)mapping one or multiple arrhythmias in a single patient with a variety of catheters
 - Manual Mapping
 - AutoMap™
 - TurboMap™
 - o Point density associated with (re-)mapping one or multiple arrhythmias in a single patient with a variety of catheters

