NOTE: The EnSite Precision™ System interfaces to either the MediGuide™ Guided Medical Positioning System or the EnSite Precision™ Module to combine and display magnetic processed patient positioning and orientation mapping information. In order to use these features, the Electrophysiologist (EP) will need to use at least one sensor enabled (SE) catheter (e.g, Advisor™ FL Circular Mapping Catheter, Sensor Enabled™ or FlexAbility™ SE Ablation Catheter) in the area or chamber of interest. Physicians or hospitals that wish to use the system without an SE catheter may do so, however the use of an SE catheter is strongly encouraged in order to take full advantage of system features.

NOTE: The EnSite™ AutoMap™ Module is a software entitlement feature within the EnSite Cardiac Mapping System. AutoMap automates the point collection process, based on the user-defined settings. As the catheter is moved, points are collected when the user-defined settings are met.

NOTE: The AutoMark feature provides the capability to visualize ablation parameter data and contact force data at the catheter tip on the EnSite Precision™ Cardiac Mapping System display. The EP can configure the software to display generator data including time, duration, power temperature and catheter dwell time.

NOTE: Any adverse event (refer to section 7.0 for details) and/or protocol deviations (refer to section 6.2 for details) at the procedure will also be recorded at this time.

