12.0 STATISTICAL CONSIDERATIONS

12.1 Statistical Design, Hypotheses, Method and Analytical Procedures

This is a multi-center, observational, prospective registry. The objective of the registry is to assess and characterize the use and performance of the EnSite Precision™ Cardiac Mapping System and EnSite Precision™ Software v2.0 (The System) in a variety of electrophysiological (EP) procedures and clinical settings.

The endpoints for characterizing and evaluating the objective are as following:

Primary Endpoints:

- EnSite Precision™ Software v2.0 Assessment
 - Accuracy of geometry: Proportion of subjects with accurate geometry
 - Overall system stability: Proportion of subjects with overall system stability
 - Unrecoverable shifts: Proportion of subjects whose map could not be recovered

- Automap™ Module Assessment
 - Mapping time associated with (re-)mapping one or multiple arrhythmias in a single subject with a variety of catheters; mapping time will be summarized (using mean, median, standard deviation, minimum and maximum across arrhythmia types, and for each type of arrhythmia as appropriate) for the following modules:
 - Manual
 - AutoMap™
 - TurboMap™
 - Point density associated with (re-)mapping one or multiple arrhythmias in a single subject with a variety of catheters; mapping points collected and used will be summarized (using mean, median, standard deviation, minimum and maximum across arrhythmia types, and for each type of arrhythmia as appropriate)

Secondary Endpoints:

- EnSite Precision™ Cardiac Mapping System Assessment
 - Ease of Use: Proportion of subjects in whom the mapping system was reported to be excellent, very good, good, poor and N/A
 - Overall Procedure time: will be summarized using mean, median, standard deviation, minimum and maximum

- AutoMark feature Assessment
 - Clinical Utility of the automated RF marker placement: proportion of subjects where the AutoMark feature assisted in identifying gaps in lesion lines
 - Ease of Use of the automated RF marker placement: proportion of subjects where the AutoMark feature was easy to use

Analysis method:

The analysis population will include subjects who have signed the Informed Consent Form and undergone the CIP defined EP study and ablation procedure. Endpoints will be summarized based on available data or measurements in the analysis population, as appropriate.

Clinical Investigational Plan

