12.2 Sample Size

It is estimated that ventricular tachycardias would occur at a rate of 10%. The study will characterize mapping time and point density for a minimum of 50 subjects with each type of arrhythmia. Since Ventricular Tachycardia is expected to occur at the lowest rate (10%), up to 500 subjects will be enrolled in this registry.

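### Mapping time is split by mapping module but mapping points are not, so a module's time difference cannot be separated from a difference in map size

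*Combined protocol and SAP*

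**What the plan says.** Section 3.4.1 of the CIP lists two primary endpoints under the AutoMap assessment: "Mapping time associated with (re-)mapping one or multiple arrhythmias in a single patient with a variety of catheters", with Manual, AutoMap and TurboMap beneath it, and "Point density associated with (re-)mapping one or multiple arrhythmias in a single patient with a variety of catheters", with no modules beneath it.

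Section 12.1 keeps that difference. Mapping time gets mean, median, standard deviation, minimum and maximum, overall and "for each type of arrhythmia as appropriate) for the following modules", after which the three modules are named. For the second endpoint, "mapping points collected and used will be summarized" with the same statistics, overall and by arrhythmia type, but no module is named. Nor is any area, volume or time denominator given, so point density is in effect a count of points.

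The note in section 5.5 describes what the module does: "AutoMap automates the point collection process, based on the user-defined settings". As the catheter moves, "points are collected when the user-defined settings are met".

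Section 12.2 names the two measures side by side: "The study will characterize mapping time and point density for a minimum of 50 subjects with each type of arrhythmia". No section plans points per minute, time to a fixed number of points, or a paired summary of time and points for the same maps. No section states a target number of points or when a map counts as complete. Under section 12.9 each endpoint uses whatever data are available, without imputation, so the two summaries need not rest on the same maps or subjects.

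**The concern.** The module acts on how fast points are collected. Faster collection can be used to finish sooner, to gather more points, or for some of each. With no stated completion rule, the CIP leaves that choice open. Mapping time by module is therefore the combined result of collection speed and map size, and the plan shows only one of the two by module.

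Two misreadings follow. A module that collects more points in the same minutes shows no time difference. A sparse map looks fast. Because points are pooled over modules, the reader cannot check either possibility, even at group level.

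At stake is what the registry can say about AutoMap. Section 3.3.1 makes characterising performance the objective, the module split invites a comparison, and section 17.0 commits the sponsor to submitting the results for publication.

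**Working it through.** **The plan's own figure.** Section 12.2 wants at least 50 subjects per arrhythmia type and takes ventricular tachycardia as the rarest, at 10%: 50 / 0.10 = 500, which matches the stated total. The point below does not change it. There is no power calculation to reproduce, because section 12.10 rules out hypothesis testing.

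**Side by side (sections 3.4.1 and 12.1).**

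| | Mapping time | Mapping points |
|---|---|---|
| Overall | yes | yes |
| By arrhythmia type | yes, as appropriate | yes, as appropriate |
| By module | yes | no |
| Joined within a map | no | no |

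All figures from here on are assumed; the documents give no mapping times or point counts.

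**Step 1. Three single maps.**
- Reference: 20 min, 100 points; 100/20 = 5.0 points per minute.
- Map A: 20 min, 400 points; 400/20 = 20.0 points per minute. Time is equal although collection is four times as fast.
- Map B: 10 min, 50 points; 50/10 = 5.0 points per minute. Time is halved although the rate is unchanged, because the map has half the points.

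If reference and A maps were equally frequent and came from different modules, the planned outputs would show 20 against 20 min by module and one pooled mean of (100 + 400)/2 = 250 points. The pooled mean does not show which module supplied the extra points.

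**Step 2. One speed gain, several time results.** Let R be the ratio of collection rates and s the share of the gain, on the log scale, that goes into extra points. Then time ratio = R^-(1-s) and points ratio = R^s. For R = 2:

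| s | Time ratio | Points ratio | Points ratio / time ratio |
|---|---|---|---|
| 0 | 0.50 (50% less) | 1.00 | 2.0 |
| 0.5 | 0.71 (29% less) | 1.41 | 2.0 |
| 1 | 1.00 (no change) | 2.00 | 2.0 |

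Time alone gives three answers for one speed. The last column recovers the speed, but it needs the points ratio by module, which section 12.1 does not plan.

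**Step 3. What separate summaries can and cannot recover.** Assume lognormal time (median 15 min, log-SD 0.6) and points (median 300, log-SD 0.8), with log-scale correlation ρ within a map.
- Mean time = 15·exp(0.6²/2) = 17.96. Mean points = 300·exp(0.8²/2) = 413.1. Their ratio is 413.1/17.96 = 23.0 per minute.
- Mean per-map rate = 20·exp[0.5(0.36 + 0.64 − 2·0.48ρ)] = 20·exp[0.5(1 − 0.96ρ)]. This is 24.7 at ρ = +0.6 and 38.1 at ρ = −0.3.
- Median per-map rate = 300/15 = 20 at every ρ.

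Under this model the ratio of medians gives the typical rate. The mean rate depends on how time and points vary together within a map, which separate summaries do not carry.

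**The case against.** The strongest reply is that points are themselves a primary endpoint, so extra points are not invisible, and that reading the two endpoints together recovers the speed. Medians are planned for both, and in step 3 their ratio is exactly the median rate. This stands as arithmetic. It does not rescue the plan as written, because points are not split by module, so the ratio cannot be formed for Manual, AutoMap or TurboMap separately. Once that split is added, the reply carries much of its weight, and the joint summary then supplies the mean and spread of the rate and a common set of maps.

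A reader might infer more than the documents support:
- *That the registry will rank the modules wrongly or fail its objective.* No ranking is planned, pass/fail criteria do not apply (12.3) and no hypothesis is tested (12.10). A comparison would be an informal reading of descriptive results, and a rate could still be derived later without statistical penalty if the data are linked.
- *That points per minute would settle the matter.* It would not. Map B in step 1 has the reference rate with half the points. The rate also depends on user-defined settings and on the catheter.
- *That linked data are missing, or certainly present.* Neither is shown. The eCRFs (Appendix G) and the Procedure Guidelines (Appendix D) are kept separately. Section 5.5 has the whole EP study returned on a USB drive, which makes linkage plausible. Both endpoints are worded for a single patient with one or several arrhythmias, so records per map are not established.

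**Conclusion.** The point holds as a gap in the planned analysis. Section 12.1 splits mapping time by module, leaves points unsplit and joins the two nowhere, so a module difference in time cannot be separated from a difference in map size. The missing module split for points is the more concrete defect, and the missing joint summary comes second.

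The size can only be illustrated. A doubled collection rate is compatible with anything from a 50% fall in mapping time to no change. Under the lognormal assumptions, the mean per-map rate runs from 24.7 to 38.1 per minute while the ratio of means stays at 23.0. How often operators trade time for points is not known from the documents.

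The consequence is for interpretation only: no error rate is involved and the total of 500 stands. The change should be made, because it is cheap and bears on a primary endpoint. The conclusion assumes that no map-completion rule or module split of points sits in the separately held guidelines or forms.

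**What to change.** In sections 3.4.1 and 12.1:

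1. Summarise points collected and points used by Manual, AutoMap and TurboMap and by arrhythmia type, with the statistics already planned for mapping time.
2. For maps with both values recorded, report time, points and points per minute together by module and arrhythmia type, giving the median as well as the mean and the number of maps contributing.
3. State that module differences in mapping time are to be interpreted alongside the point counts of the same maps, and that the rate alone does not show whether a map was complete and also reflects user settings and catheter.

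The cost is a few more descriptive rows and one derived variable, with no change to the sample size. The sponsor must first confirm that the eCRF or the USB export links time and points for each map. If neither does, item 1 may still be possible, but item 2 would need that link to be captured.
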